9.4.8.2 Adverse Events

Adverse events will be coded using the Medical Dictionary for Regulatory Activities (MedDRA) dictionary. Treatment-emergent AEs (TEAE) will be summarized for each treatment group. TEAEs are defined as AEs with a start date on or after the first dose of IMP. Frequencies and percentages of subjects with TEAEs will be calculated for each treatment group as follows:

- Any event
- By system organ class, preferred term and relationship
- By system organ class, preferred term and maximum severity
- Any event and by system organ class and preferred term for events resulting in death
- Any event and by system organ class and preferred term for events resulting in IMP discontinuation
- Any event and by system organ class and preferred term for serious adverse events
- Events of special interest (refer to Section 10.3.1)

A listing by treatment group of TEAEs grouped by body system, and preferred term with subject ID numbers will be generated. Listings of all treatment-emergent SAEs, AEs leading to death, and AEs leading to discontinuation will be generated.

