 - Change in mood or behavior includes abnormal thought, speech, and behavior after IMP administration compared with past. Such as mood extremes (depression or mania), new or worsening symptoms of anxiety or depression, and disorganized speech or behavior.

Version 6.0 82 of 138 April 11, 2024

- Infection denotes conditions with immunosuppression. This typically manifests as recurrent, severe, unusual, or opportunistic infections.
- Constant or severe headache that is distinctly different in quality from usual headaches, and may be worse at night or in the early morning, including newly happened or worsening dull, "pressure-type" headaches, sharp or "stabbing" pain. They can be localized to a specific area or generalized. They can be made worse with coughing, sneezing or straining.
 - Change in vision (and particularly loss of peripheral vision) includes dim, dark, or blurred vision or diminished peripheral vision in one or both eyes or double vision or diminished peripheral vision on one or both sides, etc.

Theoretically, PRLR blockage will increase PRL and may impact hormone excretion, however PRLR already has been blocked and it is unlikely increased PRL making functional work. Even though risks are more conceptional but need to monitor carefully during study period.

Symptoms of dopamine withdrawal

By blocking PRLR, HMI-115 will increase PRL secretion which may subsequently trigger dopamine release from hypothalamus. Any symptoms of dopamine withdrawal that have been reported after discontinuation of treatment, including apathy, anxiety, depression, fatigue, sweating and pain should be monitored. Theoretically however, PRLR on the dopamine releasing neuron is blocked, it is very unlikely that dopamine releasing will be triggered.

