1.3.2 Safety and Tolerability endpoints(s)

1.3.2.1 Adverse Events (AEs)

All AEs will be collected from the signing of informed consent form (ICF) until the end of study participation at the time points specified in the SoA (Section 1.3 of Protocol).

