8.1 Adverse Events

All AEs will be coded using the Medical Dictionary for Regulatory Activities (MedDRA) 24.0 or a later version.

Treatment Emergent Adverse Events (TEAEs) will be tabulated and are defined as those AEs with a start date on or after the first administration of IMP.

Where dates are missing or partially missing, AEs will be assumed to be treatment-emergent, unless there is clear evidence (through comparison of partial dates) to suggest that the AE started prior to the first administration of IMP. For AEs with completely unknown dates, dates will be shown as NK (unknown) in the listings. For AEs with partially start and/or end dates, the available day, month and year components will be shown in listing.

Frequencies and percentages of subjects with TEAEs will be calculated for each treatment group as follows:

- Overview incidence of all AEs
- A summary of the number and percentage of subjects reporting a TEAE by treatment, SOC, and PT
- A summary of the number and percentage of subjects reporting a TEAE by treatment, causality, SOC, and PT
- A summary of the number and percentage of subjects reporting a TEAE by treatment, severity, SOC, and PT
- A summary of the number and percentage of subjects reporting a AESI by treatment, SOC, and PT
- A summary of the number and percentage of subjects reporting a AESI by treatment, causality, SOC, and PT

Adverse event summaries will be ordered in terms of decreasing frequency for SOC, and PT within SOC, in the overall treatment groups, and then alphabetically for SOC, and PT within SOC. The actual version of the MedDRA coding dictionary used will be noted in the AE tables.

For each subject and each adverse event, the worst severity recorded will be attributed and used in the by-severity summaries. Similarly, the worst causality (most related to treatment) will be attributed and used in the by-causality summaries. If severity or causality is missing, a conservative approach for AE assessment (taking into account the worst case) will be followed.

Below listings will be provided:

- A by-subject listing of AEs
- A by-subject listing of AESIs

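### No planned AE or AESI summary counts dopamine-withdrawal symptoms arising after dosing stops or compares them with placebo, because the tables pool treatment with follow-up and do not use the protocol's AESI categories

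*SAP*

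**What the plan says.** **Time window.** SAP 8.1 describes treatment-emergent events as "defined as those AEs with a start date on or after the first administration of IMP". Protocol 9.4.8.2 has the same rule: "TEAEs are defined as AEs with a start date on or after the first dose of IMP". Neither gives an end date. SAP 1.3.2.1 sets the collection period: "All AEs will be collected from the signing of informed consent form (ICF) until the end of study participation". SAP 2.1 adds that follow-up data from women who stop treatment early are included in the analysis.

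**Tables.** For AESIs, SAP 8.1 plans "A summary of the number and percentage of subjects reporting a AESI by treatment, SOC, and PT", then "A summary of the number and percentage of subjects reporting a AESI by treatment, causality, SOC, and PT", and "A by-subject listing of AESIs". The other AE tables in SAP 8.1 and 8.2 are also laid out by SOC and PT. None is split by onset period, and none has a row for a protocol AESI category.

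**What the protocol asks for.** Protocol 9.4.8.2 points the special-interest summary to section 10.3.1. One AESI there is change in mood or behavior after IMP administration, which includes "new or worsening symptoms of anxiety or depression". Later in the same section, under its own heading, the protocol says: "Any symptoms of dopamine withdrawal that have been reported after discontinuation of treatment, including apathy, anxiety, depression, fatigue, sweating and pain should be monitored". The revision history (version 1.0 to 2.0) records that this heading was added on the U.S. FDA's suggestion. The SAP does not mention dopamine withdrawal.

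**The concern.** The two requests in protocol 10.3.1 overlap in wording. Anxiety and depression belong to both, and what separates them is whether they arise on treatment or after it ends. A table by SOC and PT over the whole study drops that information: an anxiety event on Day 20 and one on Day 110 land in the same row.

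The remaining named symptoms (apathy, fatigue, sweating, pain) carry different preferred terms and can be expected to fall under several system organ classes. No row then counts the women who had any of them.

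A reader of the study report who asks how many women in each arm had withdrawal symptoms after dosing stopped would find no table with the answer. A grouping assembled after unblinding would be open to the criticism that its terms were chosen with the results in view.

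**Working it through.** **Inputs**
- Last dose Day 71; final visit Day 169, stated as +98 days and +2352 h after the last dose (protocol Tables 1-2 and 1-3).
- EOT visit Day 85 (protocol Table 1-1).
- 38 women per arm planned (protocol 9.2). SAP section 8 sets the safety set equal to the PAS, so actual denominators may be smaller.
- Week 25 follow-up intended to cover 5 half-lives (protocol 4.4).
- Event rates: none in the documents. All rates below are assumptions.

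**1. The plan's own figure.** 169 − 71 = 98 days, and 98 × 24 = 2352 h. Both match.

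**2. Share of the pooled window that is off dosing.** After the last dose: 98/169 = 0.58. After Day 85: (169 − 85)/169 = 84/169 = 0.50.

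**3. Off dosing is not drug-free.** If 98 days is exactly 5 half-lives, the half-life is 98/5 = 19.6 days. With simple exponential decline from the last dose, the fraction left at Day 85 is 0.5^(14/19.6) = 0.61, and at Day 113 it is 0.5^(42/19.6) = 0.23. A shorter half-life would leave less.

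**4. What pooling does to an excess.** Let b be the on-treatment risk in both arms, and let w0 (placebo) and w1 (active) be the risks after dosing stops. Assume the two periods are independent and all the terms are counted together. The pooled risks are 1 − (1 − b)(1 − w0) and 1 − (1 − b)(1 − w1), so the pooled excess is (1 − b)(w1 − w0).

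| b | After dosing, placebo vs active | Pooled, placebo vs active | Excess: after dosing → pooled |
|---|---|---|---|
| 10% | 10% vs 20% | 19% vs 28% | 10 → 9 points |
| 5% | 5% vs 20% | 9.8% vs 24.0% | 15 → 14.2 points |
| 30% | 5% vs 20% | 33.5% vs 44.0% | 15 → 10.5 points |

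With a modest background, most of the absolute excess survives pooling.

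**5. What pooling does to attribution.** Reverse the first row: on-treatment risk 10% vs 20%, and 10% in both arms afterwards. The pooled risks are 1 − 0.9 × 0.9 = 19% and 1 − 0.8 × 0.9 = 28%, the same as before. The pooled table cannot tell an on-treatment mood effect from a post-dosing effect.

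**6. What scatter over terms does.** Suppose six of 38 women on one dose, and none on placebo, each have a different one of the six named symptoms. A grouped row reads 6/38 (15.8%) vs 0/38. The planned layout gives six rows of 1/38 (2.6%) vs 0/38.

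**The case against.** A reader might go further and infer that these events cannot be counted or compared with placebo at all. The documents do not support that. Preferred-term rows are shown for every arm including placebo (SAP 2.4 and 8.1), onset dates are collected, AE and AESI listings are planned, and the SAP introduction permits labelled post hoc analyses. The AESI table by causality also gives some information beyond SOC and PT, though none on timing.

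A reader might also infer that the pooled tables mix drug-exposed with drug-free time. That is not supported either: follow-up is off dosing, but drug may remain for much of it. An open-ended window is a defensible choice for a long-half-life antibody, and here the SAP follows the protocol.

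A third tempting inference is that pooling hides a signal by shrinking the risk ratio. In the first example above, the absolute excess falls by only one point, and every rate is assumed. Moreover, a pooled figure of 28% vs 19% presupposes a combined row that the plan does not contain.

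Further points stand. The withdrawal text follows the itemised AESIs under a separate heading, asks only for monitoring and calls the mechanism very unlikely, so its formal AESI status is not explicit. It refers to symptoms reported after discontinuation, which is close to, but not literally, a definition by onset. Pain is one of the named symptoms, and protocol 10.3.1 excludes expected disease symptoms from AEs unless more severe than expected; a grouped count needs a rule for this. The table shells and eCRF were not available and might hold an AESI category or period field. The DMC reviews unblinded safety data separately.

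None of this supplies the missing summary. If dopamine withdrawal is not a formal AESI, even the AESI tables would leave it out.

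**Conclusion.** The point holds as a gap in the planned summaries. Followed as written, SAP 8.1 yields no count by arm of women with dopamine-withdrawal symptoms arising after dosing stops, because the tables merge two periods (58% of study days follow the last dose) and ignore the protocol's categories. What is lost is the ability to say when events arose and which concern they belong to; the size of any pooled excess is less affected. The numerical examples rest on assumed rates and independent periods, and they show how the tables behave, not what to expect in this trial. This is a cheap improvement to descriptive safety reporting in a proof-of-concept study. It does not affect the efficacy analysis.

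**What to change.** Keep the overall TEAE tables and add the following to SAP 8.1.

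1. TEAE and AESI summaries by onset period, cut at each woman's own last dose + 14 days, which follows the exposure convention in SAP section 5. An individual cut is needed because women who stop IMP early remain in the study to Visit 10 (protocol 7.1). State on which side an onset exactly 14 days after the last dose falls.
2. One descriptive table by protocol 10.3.1 category, n (%) by arm, counting each woman once per category, with the preferred-term list fixed before unblinding. Include dopamine-withdrawal symptoms as a grouped category restricted to onset in the second period.
3. A statement of whether dopamine withdrawal is a formal AESI, and of how endometriosis pain is treated in that category.

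The cost is two extra table layouts from dates already collected. Counts per cell will be small and some drug is still present early in the second period, so the presentation should be descriptive only. The cut also places onsets in the first 14 days after the last dose in the treatment period. The protocol wording does not require that, so the SAP should state it as a convention.

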8.2 Deaths, Serious Adverse Events, and Other Significant Adverse Events

Below summaries will be provided:

- A summary of the number and percentage of subjects reporting a TEAE resulting in death by treatment, SOC and PT
- A summary of the number and percentage of subjects reporting a TEAE resulting in IMP discontinuation by treatment, SOC and PT

- A summary of the number and percentage of subjects reporting a SAE by treatment, SOC and PT
- A summary of the number and percentage of subjects reporting a SAE resulting in IMP discontinuation by treatment, SOC and PT

Listings to be provided include:

- A by-subject listing of AEs leading to death
- A by-subject listing of TEAEs leading to IMP discontinuation
- A by-subject listing of treatment emergent SAEs

8.3 Clinical Laboratory Evaluation

The following laboratory parameters will be measured for each test:

Laboratory Assessments	Parameters		
Hematology	
 • Platelet count • Hemoglobin • WBC Count (absolute) • Erythrocytes • Reticulocytes 	
 • Hematocrit • MCV • MCH 	WBC Differential: 
 • Neutrophils • Lymphocytes • Eosinophils • Monocytes • Basophils
Coagulation	
 • PT • Fibrinogen 	
 • INR 	
 • APTT
Clinical Chemistry [#]	
 • BUN • Creatinine • Glucose, fasting • Sodium • Total protein • Magnesium 	
 • Potassium • Chloride • Calcium • Albumin • GGT • Total bilirubin 	
 • AST (SGOT) • ALT (SGPT) • Alkaline phosphatase
Urinalysis	
 • Protein • Glucose • Urobilinogen 	
 • Leucocytes • Erythrocytes • Bilirubin 	
 • pH • Ketone • Nitrite • Specific gravity
Sex Hormone	
 • PRL* • DHEAS* 	
 • LH* • FSH* 	
 • Estradiol* • Progesterone* • Testosterone*
Additional Chemistry [#]	
 • FT3, FT4, TSH 	
 • CA-125 	
 • GH
Viral serology	
 • Anti-HAV • HBs Ag • HBC Ab 	
 • Anti-HCV • HCV RNA (for positive or equivocal anti-HCV) 	
 • HIV antigen • Anti-HIV (1+2)
Bone Biomarkers [#] (exploratory)	
 • CTX 	
 • P1NP 	
 • BSAP
Other tests	
 • eGFR (using CKD EPI formula) • Pregnancy test (serum pregnancy test at Visit 1 only, urine pregnancy test thereafter) • Urine drug screen: amphetamine, barbiturates, benzodiazepines, tetrahydrocannabinol, cocaine, methadone, methamphetamine, opiates, phencyclidine, and tricyclic antidepressants 		

Laboratory Assessments	Parameters
	
 Testing for COVID-19 infection (Only for subjects enrolled before protocol version 5.0): 
 SARS-CoV-2 RT-PCR (to be assessed at Screening Visit 1 and prior to randomization. Additional testing may be done depending on Investigator discretion and/or local requirements)

ALT = alanine transaminase; anti-HAV = hepatitis A virus antibody; anti-HCV = hepatitis C virus antibody; anti-HIV = human immunodeficiency virus antibodies; APTT = activated partial thromboplastin time; AST = aspartate transaminase; BSAP = bone specific alkaline phosphatase; BUN = blood urea nitrogen; CKD EPI = Chronic Kidney Disease Epidemiology Collaboration CA-125 = cancer antigen-125; COVID-19 = coronavirus disease 2019; CTX = C-terminal telopeptide of type I collagen; FSH = follicle-stimulating hormone; FT3= Free triiodothyronine; FT4 = Free thyroxine; eGFR = estimated glomerular filtration rate; GGT = gamma-glutamyl transferase; GH = growth hormone; HBsAg = hepatitis B virus surface antigen; HBcAb = Hepatitis B core antibody; DHEAS = Dehydroepiandrosterone-sulfate; INR = international normalized ratio; LH = luteinizing hormone; MCH = mean corpuscular hemoglobin; MCV = mean corpuscular volume; P1NP = procollagen type 1N-terminal propertied; PRL = Prolactin; PT = prothrombin time; RT-PCR: Real-time Reverse Transcriptase Polymerase Chain Reaction; SGOT = serum glutamic-oxaloacetic transaminase; SGPT = Serum glutamic pyruvic transaminase; SARS-CoV-2: severe acute respiratory syndrome coronavirus 2; TSH = thyroid stimulating hormone; WBC = white blood cells.

* Sex hormone samples will be collected at the menses cycle days 1 to 5. **Subjects should not take any opioids 2 days prior to blood sampling for PRL.**

Samples will be collected under morning fasting conditions.

All summaries of laboratory parameters will only summarize parameters planned based on the protocol; however, both planned and unplanned laboratory parameters will be provided in by-subject listings.

Clinical laboratory test results will be summarized descriptively for each treatment group at each visit. The within-group CFBs to each visit will be summarized and will be compared with a paired t-test for continuous measurements. The between-group difference will be compared with an ANOVA. Two-sided 95% CI will be constructed for the differences between each of the treatment groups and the placebo group in CFB.

In addition, prolactin results from sex hormone will be summarized separately for each treatment group by category the results as normal, 1 ULN to 2 ULN, 2 ULN to 3 ULN, 3 ULN to 4 ULN, >4 ULN and <1 LLN.

Shift tables for CFBs according to appropriate categories will be provided for each laboratory parameter.

By-subject listings of laboratory assessments including hematology, coagulation, clinical chemistry, urinalysis, sex hormone, additional chemistry, bone biomarker, and other tests (eGFR) will be listed. All values outside the clinical reference ranges will be flagged in the data listings. The abnormal values will be flagged with 'L' for values below the lower limit of the clinical reference range and 'H' for values above the upper limit of the clinical reference range and included in the listings.

Serum pregnancy test at Visit 1 only, and urine pregnancy test at Visits 3, 5, 7, 9 and 10. Subject with pregnancy test results will be listed.

Subjects with urine drug screen test during study will be listed.

Subjects with serology result during study will be listed.

Subjects with COVID-19 testing result will be listed.

8.4 Vital Signs, Electrocardiograms, Physical Examination, Transvaginal Ultrasound, Dual Energy X-ray Absorptiometry, and Others

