2.1 General Considerations

- 'Baseline' is defined as the last available pre-treatment assessment (including unscheduled assessments) unless otherwise specified in the SAP.
- 'End of Study (EOS)' is defined as the last available post-treatment assessment.
- 'Study Day' will be calculated relative to the date of First Administration of IMP (i.e., prior to treatment, Study Day = Assessment Date -First Administration of IMP Date; otherwise, Study Day = Assessment Date - First Administration of IMP Date+1). The day of the first IMP administration will be Day 1. In case of partial or missing event date, study day will appear missing.
- Measurements collected at early discontinuation visit (EDV) will be mapped to the scheduled visit according to the analysis visit window in Table 12.2. If EDV measurement allocates to a visit without a scheduled measurement, EDV measurement will be considered for analysis by visit. If EDV measurement allocates to a visit with existing scheduled measurement, EDV measurement will not be considered for analysis by visit. Unscheduled visits will not be mapped to scheduled visits.
- For by-visit summaries, only scheduled assessments will be used in tables, and if there are repeated post-first dose assessments, only the earlier value will be used in summary. In the subject listing, data will be presented under the nominal visits.
- Continuous data will be summarized in terms of the number of observations (n), mean, standard deviation (SD), first quartile (Q1), median, third quartile (Q3), minimum and maximum, unless otherwise stated. The minimum and maximum will be reported to the same number of decimal places as the raw data recorded in the database. The mean, median, Q1 and Q3 will be reported to one more decimal place than the raw data recorded in the database. The SD will be reported to two more decimal places than the raw data recorded in the database. In general, the maximum number of decimal places reported shall be four for any summary statistic.
- Categorical data will be summarized in terms of frequency counts and percentages. Any planned collapsing of categories will be detailed in the SAP text and the data displays.

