- Percentages will be presented to one decimal place. Percentages will not be presented for zero counts. Percentages will be calculated using n as the denominator unless otherwise specified. If sample sizes are small (n<10), the data displays will show the percentages, but any textual report will describe frequencies only.
- For quantitative measurements, change from baseline (CFB) at a particular visit will be calculated as (value at visit – baseline value).

Changes from baseline in categorical data will be summarized using shift tables where appropriate.

- P-values greater than or equal to 0.001, in general, will be presented to three decimal places after rounding. P-values less than 0.001 will be presented as "<0.001" and p-values greater than 0.999 will be presented as ">0.999".
- Confidence intervals (CIs) will be presented to one more decimal place than the point estimate.

- All values below or above a limit of quantification (e.g. <0.1 or >100) will be displayed as such in data listing. When include in table or figure summary, value may be substituted by specific value as described in corresponding section.
- For some safety parameters, the within-group and between-group differences are analyzed, but nominal p-values are provided for information only. No formal conclusion will be made based on p-values.
- For subjects who prematurely discontinued during the treatment period, their data collected during the Follow-up Period will be included in the analysis.

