7.1.2 Adjustments for Covariates

The primary efficacy analysis will be adjusted for the following covariates:

- Region (stratification variable): China, the USA and Europe
- Baseline measure of DYS measured by NRS

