7.3.5 CFB by Visit in Permitted Rescue Medication Use

Permitted rescue medication will be provided to subjects from Visit 2 for rescue use if needed for endometriosis associated pain throughout the study. Use of analgesic medication will be reported by subjects in the e-Diary on a daily basis from Visit 2 through the Follow-up period.

The average pill count of permitted rescue medications along with CFB will be summarized by visit measurement including Baseline, Week 6, Week 12 and Week 24 (following the definitions in sections of 7.2.1 and 7.3.1 for the time window). The percentage of days with analgesic rescue use which will be calculated based on those days in the visit window with non-missing data will be summarized by visit.

In addition, the pill count of rescue medications at Week 12 separated by Tier 1 and Tier 2 (following the definitions in sections of 7.2.1 for the time window) as the dependent variable, treatment comparison may be compared using an ANCOVA model with treatment and region as the main effects and baseline of pill count as a continuous covariate.

The correlation between the use of rescue medications (in terms of pill count) and DYS and NMPP measured by NRS at Week 12 measurement will be explored by summary statistics including Pearson and Spearman correlation coefficients and graphical presentation (e.g., scatter plot).

Daily use of permitted rescue medications will be listed.

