8.4.1 Vital Signs

Vital signs will be summarized descriptively for each treatment group at each visit. The within group CFBs will be summarized and will be compared with a paired t-test by visit; the between-group difference for each visit will be compared with an ANOVA, and two-sided 95% CI for the differences between each of the treatment groups and the placebo group will be presented.

A by-subject listing of vital signs will be provided.

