8.4.5 DXA Scan

Bone mineral density data from DXA scan will be summarized descriptively for each treatment group at each visit. The within-group %CFB will be summarized and will be compared with a paired t-test by visit; the between-group difference for each visit will be compared with an ANOVA, and two-sided 95% CI for the differences between each of the treatment groups and the placebo group will be presented. Data from post treatment Month 6/Month 12 (before Protocol version 5.0) will not be analyzed for clinical study report (CSR).

In addition, DXA scan will be summarized for each treatment group by category the %CFB as $\geq -3\%$, $-3\% \text{ to } -5\%$, $-5\% \text{ to } -8\%$ and $<-8\%$.

A by-subject listing of DXA scan data will be provided.

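### Between-group safety comparisons use ANOVA on change from baseline with no baseline covariate; this is valid, but less precise than the ANCOVA the SAP uses elsewhere

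*SAP*

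**What the plan says.** SAP 8.3 (laboratory tests, including hormones): "The between-group difference will be compared with an ANOVA", followed by "Two-sided 95% CI will be constructed for the differences between each of the treatment groups and the placebo group in CFB".

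SAP 8.4.1 (vital signs): "the between-group difference for each visit will be compared with an ANOVA", again with 95% CIs for each dose against placebo. SAP 8.4.3 (ECG) has the same wording.

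SAP 8.4.5 (DXA) uses the same between-group method, but on percentage change: "The within-group %CFB will be summarized and will be compared with a paired t-test by visit". Protocol 9.4.8.3 and 9.4.8.5 to 9.4.8.7 also specify ANOVA, with DXA there on change from baseline.

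These SAP sections list no model terms: no baseline covariate, and neither inclusion nor exclusion of region.

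Baseline is available. Unless otherwise specified, it "is defined as the last available pre-treatment assessment (including unscheduled assessments) unless otherwise specified in the SAP" (SAP 2.1), and the change score already needs it.

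Where the SAP wants baseline adjustment, it says so. SAP 7.1.2 opens with "The primary efficacy analysis will be adjusted for the following covariates" and names region and baseline DYS. SAP 7.3.2 does the same for NMPP. SAP 7.3.5 specifies for rescue pill counts an "ANCOVA model with treatment and region as the main effects and baseline of pill count as a continuous covariate".

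On the status of the safety tests, SAP 2.1 states: "For some safety parameters, the within-group and between-group differences are analyzed, but nominal p-values are provided for information only". It adds that no formal conclusion rests on them.

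**The concern.** Subtracting the baseline is not the same as adjusting for it. When baseline and follow-up are imperfectly correlated, the change score over-corrects: an arm that starts high by chance tends to show a larger fall. An active-minus-placebo difference in mean change therefore still moves with the chance baseline difference. ANCOVA estimates the slope from the data and removes that component.

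What is at stake is the width of the planned safety intervals. Changes in laboratory values, vital signs, ECG and BMD are listed secondary safety endpoints. The arms are small, and the documents give no precision figure for any safety contrast. SAP Section 8 also sets the safety set equal to the PAS in this version, so the number per arm may fall below 38.

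**Working it through.** **Sample size per arm.** The plan's only sizing figure is for efficacy (SAP 1.4): a paired t-test, 1-point change, SD 2.0, two-sided alpha 0.05, 80% power. This gives n = 33.4, rounded up to 34, with power 80.8%. Allowing for 10% dropout, 34/0.90 = 37.8, so 38 per arm. The stated figures reproduce. I use 34 per arm below unless stated.

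**Assumptions.** The baseline-to-follow-up correlation r is not in the documents, so a range is shown. Equal baseline and follow-up variances (σ²) and a common slope across arms are also assumed. Results are in baseline SDs.

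**Variances.**
- ANOVA on change: residual variance 2σ²(1 − r).
- ANCOVA: residual variance σ²(1 − r²).
- Ratio, ANCOVA to ANOVA: (1 − r²)/[2(1 − r)] = (1 + r)/2. The SE ratio is its square root.

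**Interval half-widths** (95%, four arms of 34, t quantiles, including the degree-of-freedom cost of the covariate):

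| r | (1 + r)/2 | SE reduction | ANOVA half-width | ANCOVA half-width | ANOVA wider by |
|---|---|---|---|---|---|
| 0.3 | 0.650 | 19% | 0.568 | 0.459 | 24% |
| 0.5 | 0.750 | 13% | 0.480 | 0.417 | 15% |
| 0.7 | 0.850 | 8% | 0.372 | 0.344 | 8% |
| 0.9 | 0.950 | 2.5% | 0.215 | 0.210 | 2% |
| 0.98 | 0.990 | 0.5% | 0.096 | 0.096 | 0.1% |

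The SE-reduction column is 1 − √((1 + r)/2), before the covariate's small cost. At 25 and 38 per arm the percentages in the last column are nearly the same.

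**Link to baseline imbalance.** The change-score difference carries −(1 − r) times the chance baseline difference. One SE of that difference is √(2/34) = 0.243 SD. It leaves 0.17, 0.12, 0.07, 0.02 and 0.005 SD in the ANOVA estimate at the five values of r.

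At 38 per arm, √(2/38) = 0.229, so a baseline difference of at least 0.3 SD has probability 2[1 − Φ(0.3/0.229)] = 0.19 per comparison. At r = 0.5 it shifts the estimate by 0.5 × 0.3 = 0.15 SD. The SE of that contrast is √(2 × 0.5) × 0.229 = 0.229 SD, so the shift is under one SE.

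**One loss, not two.** In units of σ², the ANOVA variance minus the ANCOVA variance is 2(1 − r) − (1 − r²) = (1 − r)². That is exactly the variance contributed by baseline imbalance entering with slope −(1 − r). The wider interval and the leftover imbalance are the same quantity.

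**Simulation check** (4,000 four-arm trials, 34 per arm, for each r). ANOVA intervals were wider by 23.8%, 15.1%, 8.0%, 2.2% and 0.1%. Slopes of the ANOVA estimate on the baseline difference were −0.69, −0.49, −0.30, −0.10 and −0.02; for ANCOVA they were about 0. Mean error was close to zero for both. Coverage ran from 94.6% to 95.4% for ANOVA and from 94.5% to 95.6% for ANCOVA. At r = 0.98 the ANOVA interval was the wider one in only 43% of trials.

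**The case against.** The strongest reply is that nothing here is wrong. ANOVA on change is a valid randomized comparison, protocol and SAP agree on the method, and safety p-values carry no formal weight. Much of the safety assessment rests on adverse-event incidence, shift tables, prolactin multiples of the upper limit, QTcF thresholds and BMD-loss categories, none of which adjustment touches. Unadjusted differences also reconcile with the descriptive tables. All of that stands, and it limits the point to precision. It does not remove the point, because the 95% CIs will still be reported and read.

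A reader might infer more than the documents support:

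- *That the safety comparisons are biased by regression to the mean.* Randomization balances it in expectation; it acts only through chance imbalance, which the interval already covers.
- *That these intervals are the main safety estimates.* Neither document says so.
- *That the models contain treatment only.* The terms are unstated. The PGIC ANOVA in SAP 9.3 includes region, and Protocol 9.3.1 says the stratification factors will be accounted for. Baseline is different: the SAP names ANCOVA and the covariate when it wants that.
- *That the same percentages apply to DXA.* The variance formula is for absolute change, whereas SAP 8.4.5 analyses percentage change. No document gives a correlation for BMD; if it is very stable, the gain is negligible.
- *That they apply equally to prolactin.* The protocol anticipates that prolactin may rise on drug, and SAP 8.3 tabulates values above 4 ULN, so equal variances and a common slope are doubtful.

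**Conclusion.** The point holds as a modest, nearly free gain in precision. SAP 8.3, 8.4.1, 8.4.3 and 8.4.5 list no baseline covariate, so chance baseline imbalance stays in the change-score estimates. For laboratory tests, vital signs and ECG, the intervals would be about 8% to 24% wider than ANCOVA intervals if r lies between 0.7 and 0.3, and about 2% wider at r = 0.9. For very stable measures, which may include BMD, there is almost nothing to gain.

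These sizes rest on assumed values of r, equal variances and a common slope. The planned analysis is not invalid and no formal conclusion would change. This is a desirable improvement, not a necessary correction.

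**What to change.** In SAP 8.3, 8.4.1 and 8.4.3, replace ANOVA with ANCOVA on change from baseline, with treatment and region as fixed effects and the parameter's own baseline as covariate. Make the same change in 8.4.5, on percentage change, for consistency; little gain is expected there. Report LS-mean differences with 95% CIs for each dose against placebo, and keep the descriptive change-from-baseline tables.

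For parameters with strong skew or a large drug effect on variance, such as prolactin, check the equal-variance and common-slope assumptions, for example by analysing on the log scale.

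Record the departure from Protocol 9.4.8 in SAP Section 10.

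The cost is small edits to four SAP sections and the TFL shells, and adjusted differences that will not exactly match the raw change tables. No new data are needed, and SAP 7.2.2 already contains the model form.
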